Chief Investigator: [name]

Co-investigators: [name]

Study Site

The study will take place at Hammersmith and St Mary's Hospitals, London – part of the Imperial College Healthcare NHS Trust.

Study Coordination Centre

For general queries, supply of study documentation, and collection of data, please contact:

Study Coordinator: [name]

Position: Professor of Infectious Diseases

Address: Section of Adult Infectious Disease, Imperial College London, Hammersmith Campus, [name]

[contact]

E-mail: [contact]

Clinical Queries

Clinical queries should be directed to [name] who will answer or direct the query to the appropriate person.

Sponsor

Imperial College London is the research sponsor for this study. For further information regarding the sponsorship conditions, please contact the Head of Research Governance and Integrity ([name]) at:

Head of Research Governance and Integrity [name]

[name]

[name]

[name]

[name]

[contact]

Funder

The Medical Research Council (MRC) has provided funding for this study, in conjunction with Glaxo Smith Kline (GSK). This protocol describes the above study and provides information about procedures for entering participants. Every care was taken in its drafting, but corrections or amendments may be necessary. These will be circulated to investigators in the study. Problems relating to this study should be referred, in the first instance, to the Chief Investigator.

This study will adhere to the principles outlined in the UK policy framework for health and social care research (Version 3.3, 01/11/17). It will be conducted in compliance with the protocol, the Data

Protection Act and other regulatory requirements as appropriate including Good Clinical Practice (GCP).

STUDY SUMMARY

TITLE	Adaptive immunity in older adults infected with respiratory syncytial virus
DESIGN	Human viral challenge study in healthy older volunteers
AIMS	
 1. To test the hypothesis that immune (especially T cell) responses to RSV are quantitatively and qualitatively impaired with aging 2. To identify the mechanisms underlying reduced antigen-specific cell-mediated immunity (CMI) to RSV by comparing the phenotypic and transcriptional changes in T-cells following experimental challenge with RSV in healthy older adults with young adult volunteers.
POPULATION	Healthy persons aged 18 to 40 years and 60 to 75 years. Up to 42 subjects in total
ELIGIBILITY	Healthy persons aged 18 to 40 years and 60 to 75 years that fit the inclusion and exclusion criteria
DURATION	5 years

GLOSSARY OF ABBREVIATIONS

AE	Adverse Event
BAL	Bronchoalveolar Lavage
BTS	British Thoracic Society
CI	Chief Investigator
CMI	Cell Mediated Immunity
COPD	Chronic Obstructive Pulmonary Disease
CRF	Case Report Form
CRP	C-Reactive Protein
DC	Dendritic Cell
ECG	Electrocardiogram
ELF	Epithelial Lining Fluid
ENT	Ears/Nose/Throat
FEV ₁	Forced Expiratory Volume in One Second
FVC	Forced Vital Capacity
GCP	Good Clinical Practice
GDPR	General Data Protection Regulation
GMP	Good Manufacturing Practice
GSK	Glaxo Smith Kline
HBV/HCV	Hepatitis B/C Virus
HIV	Human Immunodeficiency Virus
HRA	Health Research Authority
ICRF	Imperial Clinical Research Facility
ICRRU	Imperial Clinical Respiratory Research Unit
IMP	Investigational Medicinal Product

MRC	Medical Research Council
NHLI	National Heart and Lung Institute
NHS	National Health Service
NRES	National Research Ethics Service
PBMC	Peripheral Blood Mononuclear Cell
PCR	Polymerase Chain Reaction
PFU	Plaque-Forming Unit
PIS	Participant Information Sheet
PPE	Personal Protective Equipment
PRB	Protocol Review Board
R&D	Research & Development
REC	Research Ethics Committee
RSV	Respiratory Syncytial Virus
SAE	Serious Adverse Event
SAM	Synthetic Absorptive Matrix
SMC	Safety Monitoring Committee
SOP	Standard Operating Procedure
URI	Upper Respiratory Infection
WHO	World Health Organisation

KEYWORDS

Respiratory Syncytial Virus, RSV, immune, virus, bronchiolitis, viral challenge, viral lung disease, immunosenescence, T cells, B cells, vaccines

INTRODUCTION

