1.6. Pilot safety study

A pilot safety study will be performed to determine safety and tolerability of deliberate RSV infection in older adults.

This will be performed according to the sub-protocol “Accelerating RSV vaccine development in elderly (60-75 year old) adults by extending the controlled human infection model: a pilot safety study” (see Appendix 1-3). To ensure that the clinical team can closely monitor participant safety and to remain within the capacity of the quarantine unit, study participants will be divided into groups. The first 10 participants will be challenged in sequential cohorts as follows, with a younger sentinel group followed by older groups with pausing rules to ensure RSV disease remains within an expected mild-moderate range. Safety will be assessed at the end of quarantine (day 10 post-inoculation) for each group at which time, if no pausing criteria are met, the next group will be allowed to proceed as follows:

1. Group 1 (n=2, aged 60-67)
2. Group 2 (n=3, aged 60-67)
3. Group 3 (n=2, aged 68-75)
4. Group 4 (n=3, aged 68-75)

If any of the following pausing criteria are met, further viral challenges will be suspended until the Safety Monitoring Committee has met and approved re-commencement.

1. Occurrence of any death occurring after RSV challenge
2. Occurrence of any SAE
3. Occurrence of any unexpectedly severe disease as described in Section 1.20.1
4. Occurrence of any severe (non-serious) unexpected AE considered at least possibly related to the viral challenge

At the end of each quarantine period, the next group will be scheduled for quarantine if none of the following pausing rules is met.

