1.7. Main study

If experimental RSV infection in this age group is shown to be safe and well-tolerated in the pilot sub-study, we will move onto the main part of the study with further recruitment and implementation of the study as per protocol.

PARTICIPANT ENTRY

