1.8. Recruitment

Subjects will be recruited by advertisement in local newspapers, around College sites, the Surrey Clinical Research facility database, and online: the Imperial Trust website, Gumtree, Student Union websites, ICRF website, and on social media such as the Imperial CRF Twitter page. Additionally, respondents to adverts for prior research projects in the department will be contacted and invited to take part in our study (they have previously given their consent to be contacted). If interested, they will be invited for screening. The total number includes up to 20 in the pilot safety study. We aim to enrol up to 12 young non-smoking (18-40 year olds) and up to 30 older non-smoking (60-75 year olds) in the main study.

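### Section 1.8 places 12 young and 30 older adults in the main study, which uses all 42 places although the total is said to include up to 20 pilot participants

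*Combined protocol and SAP*

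**What the plan says.** The Population row of the Study Summary gives the overall size: "Up to 42 subjects in total", covering both age groups.

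Section 1.8 (Recruitment) makes two statements, one after the other. The first is "The total number includes up to 20 in the pilot safety study". The second sets the enrolment aim at "up to 12 young non-smoking (18-40 year olds) and up to 30 older non-smoking (60-75 year olds) in the main study".

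Section 1.6 runs the pilot under a sub-protocol titled "Accelerating RSV vaccine development in elderly (60-75 year old) adults by extending the controlled human infection model: a pilot safety study". Its six groups, of 2, 3, 2, 3, 5 and 5 people, are all aged 60-67 or 68-75.

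Section 1.7 places the main study after the pilot: if the pilot shows that challenge is safe and well tolerated, "we will move onto the main part of the study with further recruitment and implementation of the study as per protocol".

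Statistics and Data Analysis gives another recruitment aim, 32 volunteers in each group, so that at least 8 are available for each HLA type needed for tetramer work.

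**The concern.** The main-study numbers in section 1.8 add up to the overall cap, so they leave no places for the pilot that the same section counts inside the total. Section 1.7 makes it hard to treat the pilot participants as the main-study participants, because the main part comes later and recruits further people.

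Two things are at stake. First, this trial deliberately infects people aged up to 75. The maximum number challenged is a basic figure for ethics approval and safety oversight, and it should have one value. Second, pilot and main-study participants may not yield the same data. Table 1 and section 1.17 schedule bronchoscopy at Day -14, Days 7-9, Day 28 and Day 180. In section 1.6, adding bronchoscopy to the pilot is only something to discuss after the first 10 participants, and only if at least 4 are infected without safety concerns. A reader who takes 30 as the number of older adults in the main study will expect more airway data than the cap allows.

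**Working it through.** **Inputs**
- Overall cap: 42 (Study Summary).
- Pilot, counted inside the total: up to 20 (section 1.8).
- Main study: up to 12 young and up to 30 older adults (section 1.8).
- Pilot groups: 2, 3, 2, 3, 5, 5, all aged 60-75 (section 1.6).
- Aim in Statistics and Data Analysis: 32 per group.

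**Reproducing the plan's figures**
- Pilot: 2 + 3 + 2 + 3 = 10, then 10 + 5 + 5 = 20. This matches section 1.8.
- Total: 12 + 30 = 42. This matches the Study Summary, but only if no pilot place is added to it.

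**Reading A: the cap of 42 includes the pilot.** With P pilot participants and 12 young adults, the older places left for the main study are 42 − 12 − P = 30 − P.

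| Pilot size P | Main-study places (42 − P) | Older adults in main study (30 − P) |
|---|---|---|
| 10 | 32 | 20 |
| 15 | 27 | 15 |
| 20 | 22 | 10 |

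The main study reaches 30 older adults only when P = 0. With a full pilot and no young adults at all, the figure would be 42 − 20 = 22, still below 30.

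**Reading B: 12 + 30 are all main-study places and the pilot is extra.** The total challenged is 12 + 30 + 20 = 62, which is 20 above the cap.

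**Statistics and Data Analysis.** 32 × 2 = 64, which matches neither 42 nor 62. Against the ceilings in section 1.8, 32 young exceeds 12 by 20, and 32 older exceeds 30 by 2.

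**Older adults with full bronchoscopic sampling, under reading A with a full pilot.** If no pilot participant has bronchoscopy, the number is 10. If it is added for Groups 5 and 6 (5 + 5 = 10), the number is 10 + 10 = 20. This assumes that the first 10 pilot participants have none, as section 1.6 implies. The pilot appendices are not available to confirm it.

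**The case against.** The strongest reply is that the intent is plain. Section 1.8 says that the total includes the pilot, and 12 + 30 equals the summary's 42. So 30 must mean all older adults, and placing them in the main study is loose wording. The terminology helps this case: section 1.6 uses a sub-protocol, section 1.7 speaks of a pilot sub-study, and section 1.9.1 says that people who pass screening go on to the main part. This largely stands, and it settles which reading to prefer. It does not make section 1.8 correct as printed.

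It is also fair to say that every figure is a ceiling. Ceilings do not contradict each other as bare limits; they conflict only as targets to be reached together. The figure of 10 needs a full pilot and all 12 young adults. Section 1.8 also never prints 42; the link to the summary is an inference, supported by the matching sum.

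Three stronger conclusions are tempting, and the documents do not support them.
- *The trial plans to challenge 62 people.* The statement that the total includes the pilot contradicts this directly.
- *A main study with 30 older adults is impossible under any reading.* As ceilings, the figures allow several combinations. What fails is reaching the stated maxima together.
- *The age comparison loses a stated amount of power.* No section sizes an airway comparison or names a target effect for one. Any power figure would rest on a benchmark brought in from outside. It would also ignore infection: section 1.1 reports that about 55% of earlier volunteers became infected, so a comparison among infected participants would be smaller again.

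The consequence is bounded too. The primary objective is safety, and the comparison of young with older adults is exploratory (sections 1.3 and 1.5). Blood-based comparisons may be able to use older participants from both parts.

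**Conclusion.** The inconsistency is real, and it lies in a stated sample size. The cap of 42, the pilot of up to 20 inside it, and a later main study of 12 young and 30 older adults cannot all be reached together. Under the cap, with 12 young adults enrolled and a full pilot, the main study has room for 10 further older adults, a third of the printed 30. If the pilot stopped at 10, it would have room for 20. The likeliest intent is 30 older adults overall, pilot included, and the total of 62 is what section 1.8 yields only if read literally with the pilot added.

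This rests on taking the total in section 1.8 to be the 42 in the Study Summary, and on section 1.7 meaning that the main study recruits people who were not in the pilot. The aim of 32 per group remains a separate figure that fits neither total. The plan should be corrected, but the point does not show that the trial is underpowered or will exceed its cap.

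**What to change.** Correct section 1.8 to give pilot, main-study and overall numbers by age group. If the likeliest intent is right, wording such as this would do: *at most 42 people overall, made up of at most 12 young and at most 30 older adults; at most 20 of the older adults take part in the pilot, which leaves at most 10 further older adults for the main study after a full pilot.* Use the same figures in the Study Summary and section 1.7. If the sponsor did intend 30 older adults in addition to the pilot, the total must be restated and justified.

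Reconcile the aim of 32 volunteers per group in Statistics and Data Analysis with the same total, or explain what it refers to.

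Add a sentence saying that the number of older adults with full bronchoscopic sampling may be well below 30, because bronchoscopy in the pilot is conditional. Do not attach a power or detectable-difference figure to this unless the plan first defines the airway comparison, its target effect and whether it is restricted to infected participants.

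The cost is wording only, with no extra participants and no new procedures. The stated main-study number of older adults becomes less favourable.

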1.1. Background to research

Respiratory Syncytial Virus (RSV) is one of the most common causes of severe viral respiratory tract infection, second only to influenza. Despite the global burden of disease, it remains underappreciated. This is now improving as more detailed epidemiological studies are published that highlight the importance of this disease in terms of incidence, morbidity and mortality. WHO estimates put RSV as the cause of around 64 million infections each year and 160,000 deaths but this is likely to be an underestimate in view of difficulties in diagnosis. While RSV is the leading cause of severe respiratory illness in young children, it is also a major problem in adults. Incidence increases in old age, with RSV responsible for around 20% of GP visits for acute respiratory illness and up to 5% of admissions with community acquired pneumonia¹. This imposes a huge socioeconomic cost, with \$680 million spent each year in the USA for in-patient treatment alone².

Despite decades of research, there is still no specific treatment or active vaccine against RSV. Unusually, RSV does not induce long-lasting immunity following infection and therefore recurrent infections with RSV occur in all age groups with the most severe disease occurring at either end of life. While infection with a given strain of influenza may protect against symptomatic disease caused

by that same strain for up to 7 years³, even healthy adults can be repeatedly infected with an identical RSV at as little as 2 month intervals⁴.

This has hindered vaccine development as the correlates of protection that might be defined in genuinely immune individuals are not available and therefore measurements of vaccine immunogenicity remain poorly predictive of subsequent vaccine efficacy.

Antibody as a correlate of protection against RSV infection The mechanisms underlying this incomplete immunity remain unclear and factors that determine whether an individual will develop symptomatic infection following exposure to a respiratory pathogen remain ill defined. Traditionally, serum antibody has been used as a correlate of protection against many infections. However, in RSV, the protection associated with antibody is partial at best. Antibody alone does have some role in preventing severe RSV disease, as evidenced by the effectiveness of prophylactic administration of the anti-RSV monoclonal antibody palivizumab (Synagis)⁵. However, few adults are able to generate sufficiently high levels to provide consistent protection. Furthermore, some individuals with low antibody titres remain resistant to infection, suggesting that antibody-independent immune mechanisms are also important⁶. Current vaccine candidates primarily aim to induce levels of antibody higher than those generated during natural infection but it may be unrealistic to expect vaccine-induced antibody on its own to mediate complete protection.

The importance of cell mediated immunity T cells are believed to play an essential role in clearance of RSV from the lungs. In the BALB/c mouse, up to 40% of CD8+ T cells infiltrating the lung may be specific for an epitope from the M2 protein at the peak of infection⁷. Early studies in athymic nude or irradiated mice showed that persistent infection with prolonged RSV shedding could be cleared by adoptive transfer of memory T cells from previously primed animals⁸. In BALB/c mice depleted of CD4+ and CD8+ T cells, both T cell subsets play a role in shortening the duration of RSV shedding⁹. Conversely, stimulation of epitope-specific CD8+ T cells using peptide immunisation of HLA-A*0201 transgenic mice ameliorates disease and improves viral control¹⁰. Immunisation using peptide-loaded dendritic cells (DCs) from the closely related pneumonia virus of mice confers partial protection against subsequent RSV challenge¹¹. Similar findings have been observed in other animal models such as RSV infection (e.g. calves) in which depletion of CD8+ T cells delays viral clearance.

In human observational studies, T cells are also implicated in viral clearance. In children with severe infection, CD8+ antigen-specific T cells accumulate in the peripheral blood and airways, peaking at around 9 days after symptom onset¹². These display an activated phenotype, but their abundance does not correlate with disease severity. In studies of adults, numbers of activated CD4+ and CD8+ T cells do correlate with disease severity¹³. A role for T cells in viral clearance is also implied by a

prospective study examining children under the age of 5, in which individuals immunocompromised due to chemotherapy or with primary immunodeficiencies affecting T cell function were shown to suffer more severe disease and shed virus at higher levels for several months, compared with 7-21 days in normal children¹⁴. Thus it is likely that CMI is important both in shortening the duration of symptomatic disease and coordinating the generation of the overall adaptive immune response.

Aging, immune senescence and its effect on RSV infections Advancing age leads to progressive decline in immune responsiveness and alterations in immune regulation¹⁵. This contributes to increased susceptibility to infectious diseases and reduced responsiveness to vaccines. Immune responses against the vaccines commonly recommended for elderly adults are generally less robust in this population than in young adults in terms of magnitude, duration and functionality¹⁶. This usually translates to reduced vaccine efficacy¹⁷. However, the effect of aging on immune factors related to protection from symptomatic RSV disease has been relatively under-studied. Anti-RSV antibody levels are believed to be well maintained, as serum neutralising antibody titres are similar between young and old cohorts. However, low serum and nasal antibody levels have also been associated with greater risk of disease¹⁸. In addition, some groups have reported age-related reductions in antigen-specific CD8+ T cells using tetramer labelling or intracellular staining of interferon- γ following *in vitro* RSV stimulation¹⁹⁻²¹. None of these studies have correlated these observed reductions with increased risk of infection.

The importance of airway mucosal immunity RSV infects via the upper respiratory tract epithelium and severe disease is characterised by exuberant inflammation in the lower airways. Viraemia is not believed to occur and it is therefore assumed that effector mechanisms that prevent and clear RSV must act at and around the respiratory mucosa. In animal models, relative ease of access has allowed analysis of mucosal immune responses in RSV disease but in humans this has been difficult. Instead, human immune responses are most commonly investigated in blood with relatively few studies designed to investigate the unique features of immunity in the airway. Our recent work has demonstrated the role of nasal IgA in protection from RSV infection. In healthy young adults, very low levels are associated with susceptibility to infection but even at moderately high levels, protection is incomplete. Furthermore, our data indicate that RSV infection fails to induce the generation of IgA-producing memory B cells despite a robust IgG memory response, in contrast with influenza, which can induce both. These studies therefore explain the short duration of protective immunity seen following RSV infection. More detailed analysis of mucosal immune factors such as these in older adults will further define their contribution to increased susceptibility.

If viral replication overcomes the innate and humoral mechanisms that function to block infection, additional lines of defence in the airway must be mobilised to minimise tissue damage and symptoms.

In a number of peripheral tissues, the importance of the recently described CD69+CD103+ resident memory T (T_{RM}) cell subset is increasingly appreciated. Not only are CD8+ T_{RM} cells poised for immediate cytotoxicity but they may also exhibit sensing functions that provide early innate-like activity contributing to the first line of defence²². In animal models, T_{RM} cells have been shown to provide superior immune protection compared with systemic antigen-specific T cells, although their abundance in tissues may also predispose toward immunopathology²³. Our recent work using experimental human infection with RSV has demonstrated the predominance of CD8+ T_{RM} cells in the lower airway. Following RSV infection, antigen-specific CD8+ T_{RM} cells are dramatically enriched, persisting for longer and at higher frequencies than in blood. At rest, their phenotype suggests higher activation requirements in keeping with the relatively anti-inflammatory milieu of the lung, but their relatively high frequency suggests a role as patrolling cells for early defence. Since T_{RM} cells exist in tissues with little trafficking through peripheral blood, their role in immune protection against respiratory viral infections can only be assessed *ex vivo* during infection by bronchoscopy. Analysis of these cells in the controlled conditions of an experimental human infection trial will permit their correlation with risk and severity of infection.

Based on extensive preclinical and clinical research, we hypothesise that severe RSV disease (particularly in the setting of older age and pre-existing airways disease such as chronic obstructive pulmonary disease (COPD)) represents a dysregulated and over-exuberant inflammatory response to infection. Steroids have limited efficacy, and identification of druggable inflammatory pathways in severe RSV disease would be of great potential value. A number of promising clinical assets are ready for investigation, however, our ability to test novel therapeutics is limited by the currently available models of viral disease and clinical endpoints tied to disease processes. Observational studies of natural infection are constrained by sampling, timing and access. We therefore propose to extend the experimental human RSV infection studies established at Imperial College to investigate the pulmonary response to RSV infection in older adults, with the development of novel clinical endpoints which can then be used to evaluate the possible impact of treatment with validated novel anti-inflammatory agents in human RSV disease.

Safety of experimental human infections with RSV Since 2010, we have been conducting experimental human challenge studies in volunteers aged between 18 and 55. To date, 61 individuals have been inoculated safely, with around 55% subsequently developing PCR-confirmed infection. Of those, around 66% develop symptoms consistent with a common cold. The infections have been uniformly mild, self-limiting and there have been no serious adverse events.

Challenge studies overcome the many difficulties associated with studying a naturally infected patient group where diagnosis is often delayed; the timing and dose of inoculating virus is extremely variable;

many patients have underlying medical conditions influencing their immune responses; and where they may be subject to therapeutic measures that alter those responses. Using a well-characterised, fully virulent GMP-certified challenge strain of RSV will allow us to closely replicate natural infection but also provide us with the control required to answer important questions about the essential immune responses required for protection and which of these may be impaired with increasing age.

Although older adults are on average more susceptible to RSV disease, a study of natural RSV infection in adults aged 69-81 in the USA suggested that only high-risk patients (i.e. with congestive heart failure or chronic pulmonary disease) ever developed disease severe enough to require hospital treatment. Of 46 healthy older adults with virologically confirmed RSV infection, only 17% required a physician consultation and none required emergency room or hospital care. This contrasted with high-risk patients of whom 16% required hospital admission. However, it is known that older people of advanced years are at higher risk, so we have set the upper age limit at 75 years. With these safeguards, we believe the risk of severe disease in our healthy older (55-75 year old) group is likely to be low. In addition, since our study design includes a confinement period in a residential research facility (see below) signs of disease severity will be monitored very closely.

[name] and [name] in our department have already conducted several experimental infection studies in older subjects with chronic obstructive pulmonary disease using rhinovirus. These studies included volunteers aged 40-75 with post-bronchodilator FEV1/FVC <70% (i.e. moderate COPD) who were either current or ex-smokers of at least 20 cumulative pack years. As well as having been infected, these individuals also underwent multiple bronchoscopies during the course of their infections. Furthermore, these were conducted as out-patient studies without residential monitoring. Thus, rhinovirus challenge and bronchoscopy in this context have been shown to be safe even in elderly individuals with underlying lung disease and extensive smoking histories. There have never been any cases of pneumonia in volunteers for experimental respiratory infection studies at Imperial College irrespective of the virus used. Although we recognise that RSV is generally believed to cause a more severe disease in high-risk patients than rhinovirus, we believe that in a carefully screened healthy non-smoking group of older volunteers there will be no severe disease.

This study will for the first time systematically investigate the immune responses in an elderly cohort challenged with a well-defined RSV inoculum. With a global aging population and continuing difficulties in generating vaccines that can reliably induce protective immunity in the elderly, these data will indicate the targets at which development of vaccines against RSV and other infections should be directed.

